4.12. Visit Windows

Specific visit windows will not be applied to this study given the variable number of courses each patient could have received. Assessments are taken at specific study days in relation to the first day of study treatment, i.e., eryaspase: Study Day 1. Patients will continue to be treated with their preplanned chemotherapy prior to inclusion into the trial.

Analyses that consider evaluations taken up to the end of the treatment with eryaspase will consider all assessments taken up to end of consolidation/intensification period, or the day before maintenance, or sooner.

4.13. Interim Analyses

An interim analysis was planned to occur once 5 patients were included. However, an interim analysis was performed following the first 18 patients enrolled into the study and was based on soft database lock. The PK and immunogenicity were evaluated in these patients, and no formal decision was taken to stop the study. Study is being continued as planned to completion. There was no stopping rule for futility built in at the interim. The study could however be stopped early for tolerability/safety concerns.

4.14. Protocol deviations

The sponsor, or designee, will be responsible for producing the final protocol violation file (formatted as a Microsoft Excel file), in collaboration with Cytel and the data monitoring group as applicable; this file will include a description of the protocol violations, and clearly identify whether or not this violation warrants exclusion from the PP Population. This file will be finalized prior to hard database lock.

All protocol deviations will be presented in the data listings.

Sponsor:	NOPHO – Nordic Society of Pediatric Hematology & Oncology		
Protocol:	NOR-GRASPALL 2016		
Document Version No.:	2.0	Document Date:	14-May-2021

5. SUBJECT DISPOSITION, BASELINE DATA AND EXPOSURE SUMMARIES

5.1. Subject Disposition

Patients who give informed written consent but are not enrolled are considered screen failures. Minimal data, such as demographic information and the reason for screen failure.

A tabulation of patient disposition will be provided, including the number of screen failures, the number of patients enrolled, the number in each subject population for analysis, and the primary reasons for withdrawal from treatment and study. Disposition will also be summarized by study site. Reasons for screen failure will also be summarized.

A CONSORT diagram showing the flow of the participants through each stage of the study will be provided. A complete accounting of all patients participating in the study will be provided in overall summary table(s). This will include the final disposition of all study patients including the number of:

- Screen failures
- Patient enrolled
- Patients completed the intended courses of asparaginase therapy (both PEG-ASNase and eryaspase)
 - Completed first dose of therapy
 - Completed two doses of therapy
 - Completed 3 doses of therapy
 - Completed 4 doses of therapy
 - Completed 5 doses of therapy
 - Completed 6 doses of therapy
 - Completed 7 or more doses of therapy
- Discontinuation prior to completing planned therapy by primary reason (adverse reaction, other AEs, investigator's decision, patient's decision), relapse, death, others
- All deaths, including the follow-up period
- Deaths on study (during treatment or within 30 days of the last dose of study drug)

Distribution of patients by investigator with respect to the number of patients enrolled will be presented.

A by-subject listing of study completion information, including the reason for premature treatment and study discontinuation, if applicable, will be presented.

Sponsor:	NOPHO – Nordic Society of Pediatric Hematology & Oncology		
Protocol:	NOR-GRASPALL 2016		
Document Version No.:	2.0	Document Date:	14-May-2021

5.2. Demographic and Baseline Characteristics

5.2.1. Demographic Data

Demography and baseline data will be summarized using descriptive statistics.

Demographics and inclusion data on Day 1 will be analyzed on the main study analysis population. A descriptive analysis will present the following variables:

- Gender: (Male/Female), Number and % of patients
- Age (years, range, median, mean)

Age will be calculated in years without decimal figures according to the formula: $[INT(date of Visit 1 - date of birth)/365.25)]$, with $INT(X) =$ whole part of X
- Age group

Classes will be defined as the followings: Children <18 years old / Adults (≥ 18 years old)

Frequency tables and/or summary tables will be provided for the following assessments:

Body Mass Index (BMI [kg/m²])

5.2.2. Disease Characteristics and ALL History

The following baseline characteristics and ALL history will be summarized for the Evaluable and PP populations, and by age class [Children <18 years old)/Adults (≥ 18 years old)]:

- Time since primary diagnosis of ALL, calculated in month, with 1 decimal
- Immunophenotype (B cell, T cell)
- Failure to 1st line treatment (yes/no)
- Site of disease
 - Medullary
 - Extra medullary:
 - CNS status (not done, no blast cells, Blast cells + WBC < 5 per uL, Blast cells + WBC ≥ 5 per uL)
 - Combined
- Allergic reactions to prior asparaginase treatment

Sponsor:	NOPHO – Nordic Society of Pediatric Hematology & Oncology		
Protocol:	NOR-GRASPALL 2016		
Document Version No.:	2.0	Document Date:	14-May-2021

- Worst Grade (Grade 1, Grade 2, Grade 3, Grade 4)
- Silent inactivation
- Combined allergic reactions and silent inactivation
- Anti-asparaginase antibody status at baseline

5.2.3. Medical History

Medical history will be coded using MedDRA dictionary, Version 21.0

The number and % of patients presenting at least with one relevant medical condition will be presented.

The relevant medical condition will be presented per System Organ Class (SOC) and Preferred Term (PT)

The number and frequency of patients presenting with at least relevant medical condition, also presented by SOC and PT. Medical history of the same nature will be pooled together, examples are presented below:

- Transaminases increased: ALT, AST and Transaminases.
- Anemia: Anemia, hemoglobin decreased.
- Thrombocytopenia: Thrombocytopenia, platelet count decreased.
- Leukopenia: Leukopenia, white blood cells count decreased.
- Leukocytosis: Leukocytosis, white blood cells count increased.
- Hyperglycemia/Diabetes: Hyperglycemia, Diabetes mellitus, Diabetes mellitus inadequate control, Type 2 diabetes mellitus, blood glucose level increased.
- Hypertriglyceridemia: Hypertriglyceridemia, triglycerides increased.
- Liver injury: Liver injury, drug-induced liver injury, hepatocellular injury, Veno-occlusive liver disease.
- Hyperuricemia: Hyperuricemia, blood uric acid increased.

In case of partial or missing end date, medical history will be assumed to be ongoing except if the partial date indicates that the condition stopped prior to the selection visit.

Sponsor:	NOPHO – Nordic Society of Pediatric Hematology & Oncology		
Protocol:	NOR-GRASPALL 2016		
Document Version No.:	2.0	Document Date:	14-May-2021

5.2.4. Concomitant medications:

The concomitant treatments will be coded in function of the ATC classification, using the WHO Drug dictionary, version B3 June 2018. All the treatments will be listed according to the therapeutic class.

Concomitant treatments during the study will be presented by Therapeutic Class and Preferred Term (PT) in a frequency table of the safety population.

Sponsor:	NOPHO – Nordic Society of Pediatric Hematology & Oncology		
Protocol:	NOR-GRASPALL 2016		
Document Version No.:	2.0	Document Date:	14-May-2021

6. STATISTICAL ANALYSIS

6.1. Analysis of the primary endpoint

The primary population for analysis will be the Evaluable Patient population defined as all patients recruited into the study who provide data on whole blood ASNase activity on Day 14 (+/- 2 days) following the first administration of eryaspase.

A formal statistical hypothesis test will be performed on the primary endpoint. A single sample binomial test will be used to test the null hypothesis at the 2.5% one-sided significance level.

Descriptive statistics will be presented. For binary endpoints, 95% confidence intervals for the observed proportions will be calculated using Wilson Score method.

6.2. Analysis of Key Pharmacokinetic Secondary Endpoints

6.2.1. Pharmacokinetic Parameter Calculations

Pharmacokinetic parameter analyses will be conducted using the Pharmacokinetic Population. The pharmacokinetic parameters to be determined are summarized below, Table 3:

Table 3 **Pharmacokinetic Parameters for Analysis**

Parameter	Description
Cmax	Maximum observed concentration after each administration
tmax	Time corresponding to occurrence of Cmax
Ctrough	Observed concentration at the end of each dosing interval
t1/2	Apparent terminal elimination half-life
AUC(0-t)	AUC from time zero to the last quantifiable concentration
AUC(0-inf)	AUC from time zero extrapolated to infinity following first administration
%AUCex	Percentage of AUC(0-inf) obtained by extrapolation following first administration
MRT	Mean Residence Time
CL	Clearance following first administration
Vss	Volume of distribution following first administration

Sponsor:	NOPHO – Nordic Society of Pediatric Hematology & Oncology		
Protocol:	NOR-GRASPALL 2016		
Document Version No.:	2.0	Document Date:	14-May-2021

PK parameters will be calculated by non-compartmental analysis (NCA) methods from the whole blood concentration-time data using Phoenix WinNonLin version 8.0 and following these guidelines:

- Actual sampling times relative to dosing rather than nominal times will be used in the calculation of all derived PK parameters.
- There will be no imputation of missing concentration data.
- Any subjects with missing concentration data will be included in the PK analysis set provided that at least Cmax and AUC(0-t) can be reliably calculated
- All below the limit of quantification (BLQ) values pre-dose will be substituted by zeros; thereafter, BLQ values between evaluable concentrations will be set to missing
- PK parameters will be estimated according to the following:
 - Cmax and Ctrough will be obtained directly from the concentration-time data.
 - tmax is the time at which Cmax is observed.
 - The terminal phase rate constant (λz) will be estimated by linear regression after log-transformation of the concentrations:
 - Only those data points that are judged to describe the terminal log-linear decline will be used in the regression.
 - A minimum number of three data points in the terminal phase will be used in calculating λz with the line of regression starting at any post-Cmax data point

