8.4.1 Total Asparaginase Activity

Blood samples will be drawn to determine asparaginase activity as follows:

Courses with dose every 2 weeks:

- 15 min (\pm 5 min) before eryaspase administration
- End of infusion (0-10 min)
- 24 hours post-infusion (\pm 2 hrs)
- 3 days (\pm 1 day) post-infusion
- 6 days (\pm 1 day) post-infusion
- 10 days (\pm 2 days) post-infusion
- 14 days (\pm 2 days) post-infusion. The 14-day post-infusion sampling corresponds with the pre-eryaspase for next dose (i.e., the Day 15 sample for dose 1 = the pre-dose sample for dose 2, etc.)

Courses with dose every 6 weeks:

- 15 min (\pm 5 min) before eryaspase administration
- End of infusion (0-10 min)
- 24 hours post-infusion (\pm 2 hrs)
- 3 days (\pm 1 day) post-infusion
- 6 days (\pm 1 day post-infusion
- 10 days (\pm 2 days) post-infusion

- 14 days (\pm 2 days) post-infusion
- 21 days (\pm 2 days) post-infusion

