6.2.2. Pharmacokinetic Tables, Figures and Listings

Pharmacokinetic concentration data will be listed by subject including actual sampling times relative to dosing. Whole blood ASNase concentrations will be summarized by dosing course. The following descriptive statistics will be presented for concentrations obtained at each nominal time point: n, arithmetic mean, SD, coefficient of variation (CV%), median, minimum and maximum values.

Pharmacokinetic parameters will be listed by subject and summarized by course following the first and fourth infusion of the 2-week regimen. Descriptive statistics for calculated PK parameters will include n, arithmetic mean, SD, CV%, geometric mean, median, minimum, and maximum values. For t_{max}, only median, minimum, and maximum values will be presented.

Individual whole blood concentration versus actual times will be plotted by course in linear and semi-logarithmic scale. Mean and median concentrations versus nominal times will also be presented in linear and semi-logarithmic scale by course.

All concentrations below the limit of quantification (BLQ) or missing data will be labeled as such in the concentration data listings. Missing samples will be reported as no sample ("NS") and excluded from analysis. Values that are BLQ will be substituted with zero for the calculation of descriptive statistics of concentration by time point and will be displayed as "not calculable" or NC for the calculation of statistical summaries.

For graphs of arithmetic means and medians, all BLQ mean concentrations will be substituted by zeros. Any arithmetic mean or median that is BLQ will be excluded from log/linear presentation. Any BLQ values prior to the last quantifiable concentration will be plotted as zero for individual linear/linear graphs and excluded from log/linear graphs. All BLQ values after the last quantifiable concentration will be excluded from individual linear/linear and log/linear graphs.

All analyses will be based on the Pharmacokinetic Population.

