6.3.2. Other Pharmacodynamic Endpoints

Levels of cytotoxic methotrexate (MTX polyglutamates) and 6-mercaptopurine metabolites (6-thioguanine nucleotides, 6TGN, and methylated metabolites, MeMP) and of DNATGN levels in circulating leukocytes will be summarized over time using descriptive statistics.

Additional exploratory analyses include:

- Correlating serum albumin levels at D14 with Cmax and AUC at steady state.

These two endpoints will be presented in a scatterplot with ASNase activity at Day 14, and Pearson's correlation coefficient will be calculated for each endpoint.

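### The SAP defines no AUC over the 14-day dosing interval, so the only AUC available after infusion 4 ends wherever each patient's last quantifiable sample falls

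*SAP*

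**What the plan says.** SAP Table 3 lists two AUCs. AUC(0-t) is "AUC from time zero to the last quantifiable concentration". AUC(0-inf) is "AUC from time zero extrapolated to infinity following first administration". Neither the SAP nor Protocol 12.4, which prescribes the trapezoidal rule, defines an AUC over a fixed interval.

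The rules that determine where AUC(0-t) ends are these:

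- **Time basis (SAP 6.2.1):** "Actual sampling times relative to dosing rather than nominal times will be used in the calculation of all derived PK parameters".
- **Last sample of a 2-week course (Protocol 8.4.1):** 14 days with a tolerance of 2 days. The same section adds: "The 14-day post-infusion sampling corresponds with the pre-eryaspase for next dose".
- **Missing samples (SAP 6.2.1):** "There will be no imputation of missing concentration data", and "Any subjects with missing concentration data will be included in the PK analysis set provided that at least Cmax and AUC(0-t) can be reliably calculated".
- **Pharmacokinetic Population (SAP 4.6.4):** Cmax, AUC(0-t) and Ctrough must be evaluable after the first infusion. Nothing is required of infusion 4.

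On use, SAP 6.2.2 states: "Pharmacokinetic parameters will be listed by subject and summarized by course following the first and fourth infusion of the 2-week regimen". SAP 6.3.2 plans an exploratory analysis: "Correlating serum albumin levels at D14 with Cmax and AUC at steady state". Table 3 has no parameter of that name.

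**The concern.** AUC is named in the primary objective (Protocol 3.1, SAP 2.1), and the SAP reports it after infusions 1 and 4. A reader will naturally set those two summaries side by side to judge exposure across courses. After infusion 4 only AUC(0-t) is available, and its upper limit depends on when the last usable sample was drawn. A late closing sample makes exposure look higher, and a missing one makes it look lower, with no difference in how the drug behaves. The same floating quantity may enter the albumin correlation as the steady-state AUC, because the SAP does not say which AUC is meant.

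**Working it through.** The documents give no figure to reproduce here, so the check asks how far AUC(0-t) moves when only the end time changes.

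**Inputs.** The permitted last sample is Day 12 to Day 16, and the preceding scheduled sample is Day 10 (Protocol 8.4.1). The half-life h is an assumption: 7 to 14 days, with 5 to 20 days as a wider range.

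**Formula.** With mono-exponential decline every patient has the same curve, and AUC(0-t) is proportional to 1 − 2^(−t/h). So

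AUC(0-t) / AUC(0-14 d) = (1 − 2^(−t/h)) / (1 − 2^(−14/h)).

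The denominator is 1 − 0.25 = 0.75 for h = 7 and 1 − 0.5 = 0.5 for h = 14. Carry-over from earlier doses scales the whole curve after infusion 4, so the ratio holds there too.

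| Last sample | h = 7 d | h = 14 d | Status |
|---|---|---|---|
| Day 10 | 0.838 | 0.781 | Day-14 sample missing |
| Day 12 | 0.927 | 0.896 | within window |
| Day 16 | 1.060 | 1.094 | within window |
| Day 21 | 1.167 | 1.293 | outside the 2-week schedule |

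**Spread if every Day-14 sample is in window.** With last-sample times simulated uniformly over Days 12 to 16, identical patients show an artificial coefficient of variation of 2.7% (h = 5 d) to 6.4% (h = 20 d). The mean barely moves (0.998 to 0.999 of the true value). If 10% of Day-14 samples are missing (an assumption), the coefficient rises to between 4.9% and 9.9%.

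**Setting infusion 4 beside infusion 1.** The true AUC(0-14 d) ratio is the sum of 2^(−14k/h) for k = 0 to 3.

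| | h = 7 d | h = 14 d |
|---|---|---|
| True ratio | 1.33 | 1.88 |
| Infusion 1 ends Day 16, infusion 4 ends Day 12 | 1.16 | 1.54 |
| Infusion 1 ends Day 12, infusion 4 ends Day 16 | 1.52 | 2.29 |
| Infusion 1 ends Day 14, infusion 4 ends Day 10 | 1.11 | 1.46 |

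These rows are extremes for a single patient, not expected shifts in a group mean.

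**Can AUC(0-inf) stand in?** Not after infusion 4, where it is not planned. After infusion 1 its share beyond Day 14 is 2^(−14/h), which is 25% for h = 7 and 50% for h = 14. The SAP sets no limit on %AUCex.

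**The case against.** The strongest reply is that little depends on this AUC. The SAP plans no ratio, paired contrast or test between infusions 1 and 4. It judges steady state by inspecting trough values (6.2.1), and it summarises Cmax, Ctrough and nominal-time concentrations by course as well. SAP section 9 moves the PK parameters to secondary endpoints, and clearance uses AUC(0-inf) after infusion 1. The window is symmetric around Day 14, so group means are nearly unaffected when samples are taken on schedule. All of this stands and limits the importance of the point.

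Infusion 1 is also better protected. AUC(0-inf) is reported there, and SAP 4.6.4 requires an evaluable trough. That protection is less firm than it looks, because the inclusion rule in SAP 6.2.1 asks only for Cmax and AUC(0-t); the two rules should be reconciled. Equally, a profile that ends early because activity fell below quantification reflects the drug, not the schedule.

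A third reply is that extending a curve to Day 14 conflicts with SAP 4.6.4, which bars imputation in PK analyses. It does not defeat the remedy. The SAP already extends curves with lambda-z to obtain AUC(0-inf). It does mean the text must say so and provide for cases where lambda-z cannot be estimated.

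A reader might go further and infer that AUCs could differ by 39 to 66% from timing alone, by setting a Day-21 end point against a Day-10 one (1.167/0.838 = 1.39; 1.293/0.781 = 1.66). The documents do not support that as a description of this trial. Protocol 8.4.1 schedules a Day-21 sample only in 6-week courses. Reaching Day 21 in a 2-week course needs a delayed dose, for which no frequency is given, or a sampling schedule after infusion 4 that the text does not settle: note h to the SAP 3.4 schedule lists 21 days among the times for each course. Nor do the documents support reading this as a threat to the formal tests.

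**Conclusion.** The point holds as a gap in a descriptive analysis. No dosing-interval AUC is defined, and AUC(0-t) can differ between patients and courses even when kinetics are identical. Relative to AUC(0-14 d), the artefact is about −7 to −10% for a Day-12 last sample and +6 to +9% for Day 16. It is −16 to −22% when the Day-14 sample after infusion 4 is missing and Day 10 is last. These sizes rest on mono-exponential decline and an assumed half-life of 7 to 14 days. How often the Day-14 sample is missing is unknown.

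The effect is confined to secondary PK summaries and the exploratory albumin correlation in SAP 6.3.2, where the steady-state AUC is undefined. AUC(0-t) is the only Table 3 AUC available for that correlation, but the wording could equally mean a dosing-interval AUC. The primary and key secondary endpoints are proportions based on Day-14 activity and are untouched. This is a worthwhile, inexpensive improvement.

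**What to change.** 1. Add a row to SAP Table 3: AUC(0-14 d), that is AUCtau for the 2-week regimen, calculated in WinNonlin as a partial area to exactly 14 days.
2. Where the profile runs past Day 14, interpolate. Where it ends earlier, extend from the last quantifiable value with lambda-z, but only if lambda-z meets the criteria in SAP 6.2.1 (at least three terminal points, and the adjusted R² rule). Otherwise report the value as not calculable.
3. Flag every extended value in the listing, and state whether the Day-14 value was missing or below quantification.
4. State in SAP 4.6.4 that this extension, like the one for AUC(0-inf), is not missing-data imputation. Align the trough requirement there with the inclusion rule in 6.2.1.
5. Summarise AUC(0-14 d) at infusions 1 and 4, and name it as the steady-state AUC in 6.3.2. Keep AUC(0-t) for the listings and for %AUCex.

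With a fixed interval, identical mono-exponential profiles give a ratio of 1.00 to AUC(0-14 d) whatever the sampling day.

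**Cost.** One table row, a few sentences and a software setting; no new data. The downsides are a few days of model-based area for profiles that end early (16 to 22% of the interval AUC for a Day-10 end, under the assumed half-lives) and some non-calculable values. A fixed interval does not remove the effect of delayed doses on carry-over into infusion 4.

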6.2.2. Pharmacokinetic Tables, Figures and Listings

Pharmacokinetic concentration data will be listed by subject including actual sampling times relative to dosing. Whole blood ASNase concentrations will be summarized by dosing course. The following descriptive statistics will be presented for concentrations obtained at each nominal time point: n, arithmetic mean, SD, coefficient of variation (CV%), median, minimum and maximum values.

Pharmacokinetic parameters will be listed by subject and summarized by course following the first and fourth infusion of the 2-week regimen. Descriptive statistics for calculated PK parameters will include n, arithmetic mean, SD, CV%, geometric mean, median, minimum, and maximum values. For t_{max}, only median, minimum, and maximum values will be presented.

Individual whole blood concentration versus actual times will be plotted by course in linear and semi-logarithmic scale. Mean and median concentrations versus nominal times will also be presented in linear and semi-logarithmic scale by course.

All concentrations below the limit of quantification (BLQ) or missing data will be labeled as such in the concentration data listings. Missing samples will be reported as no sample ("NS") and excluded from analysis. Values that are BLQ will be substituted with zero for the calculation of descriptive statistics of concentration by time point and will be displayed as "not calculable" or NC for the calculation of statistical summaries.

For graphs of arithmetic means and medians, all BLQ mean concentrations will be substituted by zeros. Any arithmetic mean or median that is BLQ will be excluded from log/linear presentation. Any BLQ values prior to the last quantifiable concentration will be plotted as zero for individual linear/linear graphs and excluded from log/linear graphs. All BLQ values after the last quantifiable concentration will be excluded from individual linear/linear and log/linear graphs.

All analyses will be based on the Pharmacokinetic Population.

